1.1 Objective(s)

The current study aims to explore the functional use of LFPs recorded intraoperatively for the optimization of a directional DBS lead programming

Aim-1: To determine whether intraoperative LFPs recorded from the segmented DBS electrode can predict the optimal stimulation parameters.

Aim-2: Compare the therapeutic window for stimulation delivered through directional and conventional leads and determine if the spatio-spectral LFP patterns correlate with the presence of stimulation side effects.

1.2 Devices Used

The following devices will be used in this clinical investigation:

Device name	Model/Type	Manufacturer	Region/ Country	Investigational or Market Released
Infinity IPGs	6660 -3	Abbott	US	Market released
Infinity Directional Leads	6170-3	Abbott	US	Market released
Infinity System Extensions	6371-3	Abbott	US	Market released
Guardian™ Burr Hole Cover	6010	Abbott	US	Market released
Clinician Programmer	3872 & 3874	Abbott	US	Market released
Patient Controller	6883 & 3875	Abbott	US	Market released
DBS EPG	6599	Abbott	US	Market released
8-Channel Adapters	2311 & 2316	Abbott	US	Market released
Multilead Trial Cable	3014	Abbott	US	Market released

1.3 Indications for Use

The Infinity directional leads are indicated for use in DBS as treatment for PD symptoms.

1.4 Design

This is a feasibility study designed to evaluate the usefulness of intraoperative LFP recordings obtained from the implanted DBS lead to predict ideal stimulation parameters.

Additionally this study will compare the therapeutic window for stimulation delivered through directional and conventional leads and determine if the spatio-spectral LFP patterns correlate with the presence of stimulation side effects.

Approximately 8 subjects will be enrolled in this clinical investigation. The clinical investigation will be conducted at 2 centers in the USA.

Subjects participating in this clinical investigation will be monitored during DBS implant procedure and programming. The expected duration of enrollment is 8 months. The total duration of the clinical investigation is expected to be 1 year.

1.5 Endpoints

The overall goal of the study is to investigate LFP analysis as a strategic tool in the operating room (OR) setting and to establish the relationship between LFPs and DBS efficacy and side effects.

1.5.1 Primary Endpoints

Concordance between LFP derived predictions and clinically optimized stimulation parameters

1.5.2 Secondary Endpoints

Characteristic of the LFP signals correlating to presence of side effects

1.6 Study Population

In this study we will explore the predictive capacity of LFPs recorded from STN. In total, 8 patients undergoing bilateral STN DBS and part of the PROGRESS study will be enrolled for this investigation over a 1-year period. The current surgical case load at BCM supports this level of enrollment. The details of implantation procedures and blinded trial design are given in the following sections.

1.7 Inclusion/Exclusion Criteria

1.7.1 Inclusion Criteria

- Patient currently enrolled in the PROGRESS study
- Age 18-70 years
- Ability to provide informed consent
- Diagnosis of idiopathic Parkinson's disease, and DBS consensus team review supporting the placement of STN DBS.

1.7.2 Exclusion Criteria

- Subject is not a surgical candidate;
- In the Investigator's opinion the subject unable to tolerate multiple programming sessions within a single setting;
- Subject unable to comply with the follow-up schedule

1.8 Enrollment

A patient becomes a subject once he/she has been fully informed about the study, has agreed to participate, signed & dated the consent.

1.9 Study Assessments

LFP recordings will be collected from the implanted DBS lead at the end of the DBS implantation procedure. Simultaneously other biomedical and physiological signals collected with a variety of sensors, including a 2-channel bipolar electrocardiogram, 4 channel electromyogram (EMG; 2 upper and 2 lower limbs), and two 3-axis accelerometers attached to contra-lateral limbs.

The optimal stimulation parameters, selected using standard clinical programming algorithms, will be collected for comparison with the predictions obtained from the analysis of the data collected during the DBS implant procedure.

2 Introduction

The current study aims to explore the functional use of LFPs recorded intraoperatively for the optimization of a directional DBS lead programming via the following two aims:

Aim-1: To determine whether intraoperative LFPs recorded from the segmented DBS electrode can predict the optimal stimulation parameters.

Aim-2: Compare the therapeutic window for stimulation delivered through directional and conventional leads and determine if the spatio-spectral LFP patterns correlate with the presence of stimulation side effects.

This clinical investigation will be performed in the U.S.A. and is sponsored by Abbott.

This clinical investigation will be conducted in accordance with this CIP. All parties involved in the conduct of the clinical investigation will be qualified by education, training, or experience to perform their tasks and this training will be documented appropriately.

3 Background and Justification for Clinical Investigation

The efficacy of deep brain stimulation (DBS) has been established and it is now the most commonly used surgical treatment for patients with Parkinson's disease (PD) in the U.S. DBS provides patients with moderate to advanced symptoms a better quality of life than with medication alone (Deuschl et al., 2006; Williams et al., 2010). There is no consensus as to the optimal site for the active electrode of the DBS lead in the subthalamic nucleus (STN). Additionally, patients receive differing therapeutic benefit with varying DBS parameters. Consequently, quantitative and objective methods for determining optimal electrode location and stimulation parameters are needed (Mera et al., 2011). STN stimulation can result in side effects arising from the spread of stimulation to surrounding structures (Richardson, et al., 2009). Moreover, sub-optimal positioning of DBS electrodes accounts for up to 40% of cases of inadequate efficacy of stimulation postoperatively (Okun et al., 2005). Thus, the clinical efficacy of DBS depends critically on accurate localization of the STN and generated stimulation field.

DBS surgery in PD involves the stereotactic implantation of a macroelectrode into a pre-determined target region, selected based on the indication being treated. The indirect, or consensus target coordinates are then modified based on preoperative stereotactic imaging and/or intraoperative electrophysiological techniques. The most commonly employed electrophysiological techniques include microelectrode recording and macrostimulation through the DBS electrode. Microelectrode single unit activity (SUA) recording allows the identification of individual neurons that are characteristic of the target of interest, by virtue of cellular firing rate, amplitude, pattern, and distance from the cortical surface. The DBS electrode, which typically consists of four platinum-iridium contacts, is subsequently implanted based on the microelectrode findings. Implantation of DBS electrodes also makes it possible to assess the neural activity of a population of neurons from deep brain structures. Therefore, local field potentials (LFPs) can be used strategically to study the dynamics of deep brain structures and develop novel technologies for the improvement of DBS therapy in a closed loop fashion.

Our hypothesis are that a) current steering will yield fewer side effects than omnidirectional stimulation and b) the knowledge about the spatial distribution of LFPs assessed with segmented leads can be used to select certain stimulation parameters.

With these motivations we will study the following aims to explore the functional use of LFPs recorded intraoperatively for the optimization of a directional DBS lead programming. A schematic diagram representing our proposed work is also given in Fig.1.

Studies measuring and analyzing the LFPs in the STN indicate that excessive synchronization of oscillatory activity exists in the beta frequency band (8–30Hz) and can be used as a possible pathophysiological marker of the Parkinsonian state in human patients with PD (Brown et al., 2001; Williams et al., 2002; Kuhn et al., 2005). It is well recognized that PD patients in the “off” medication state demonstrate increased power in beta band oscillations at rest in both the STN and the GPi (Brown and Williams, 2005). Levodopa intake, and subsequent motor improvement, correlates with the power decrease of the beta band in both the STN (Kuhn et al, 2009) and GPi (Brown et al, 2001). However, limited research explored the functional use of LFPs for the optimization of DBS in the clinical setting. The latest research executed on a small population of human subjects indicates that the LFP activity recorded post operatively can serve as a neuro-biomarker to predict the optimal contact for stimulation (Ince et al., 2010).

With this motivation, the LFPs recorded from the contacts of the segmented DBS electrode located in the STN will be used to investigate whether the assessed activity during the surgery can be correlated with the magnitude of symptom severity and improvement following stimulation. **Specifically, through a blinded study, we will investigate whether the contacts with excessive LFP activity at various bands seen intra-operatively match the contacts selected clinically for DBS programming. If they do not match, contributing factors will be explored.** A sample dataset representing the predictive capability of intra-operative STN LFPs to select the clinically optimal stimulation contact is given in Fig.2.

[figure not shown]
[figure not shown]

Fig.1. The schematic diagram of our blinded study design is given in the top image. The LFP and SUA recording will be obtained in the OR and information obtained from both modalities will be used for track selection. Intraoperative LFP recordings will be obtained simultaneously with SUA from three trajectories identified by stereotactic imaging (A). The microelectrodes will be inserted towards the estimated target with a Neurodrive (B) to localize characteristic SUA or excessive LFP activity in the STN (D). After the identification of optimal track and depth, a directional DBS electrode (E) with 1-3-3-1 configuration will be implanted temporarily. LFP recordings will be obtained from all 8 contacts of the directional lead and will be processed in real-time intraoperatively with a system developed in [name] laboratory. The neurologist will be blinded to these LFP recordings (F). The therapeutic window will be studied with the implanted electrode by generation of the stimulation with 6 unidirectional and one omnidirectional pattern (G and E). The outcome of the unidirectional stimulation will be

4 Device(s) Under Investigation

4.1 Identification and Description of the Devices under investigation

4.1.1 Identification

No devices are under investigation in this study. In this study we seek to evaluate the feasibility of using LFP recorded during DBS lead implant as support to programming of DBS stimulation parameters. This will be performed using custom software for analysis of electrophysiological data developed by [name].

Table 1: Identification of Devices under Investigation

Device name	Model/Type	Manufacturer	Region/ Country	Investigational or Market Released
Infinity IPGs	6660 -3	Abbott	US	Market released
Infinity Directional Leads	6170-3	Abbott	US	Market released
Infinity System Extensions	6371-3	Abbott	US	Market released
Guardian™ Burr Hole Cover	6010	Abbott	US	Market released
Clinician Programmer	3872 & 3874	Abbott	US	Market released
Patient Controller	6883 & 3875	Abbott	US	Market released
DBS EPG	6599	Abbott	US	Market released
8-Channel Adapters	2311 & 2316	Abbott	US	Market released
Multilead Trial Cable	3014	Abbott	US	Market released

4.1.2 Device Description and Intended Purpose

The Infinity device and all the devices indicated in table 1 are indicated for use in the treatment of Parkinson's disease.

4.1.3 Device Handling and Storage

Sponsor requires all investigational products be stored, according to the labeling and Instructions for Use, in a secure area to prevent unauthorized access or use.

4.2 Devices Accountability

Post market study not requiring device accountability.

5 Clinical Investigation Design

5.1 Clinical Investigation Design

This is a prospective single center feasibility trial aimed at evaluating the functional use of LFPs recorded intraoperatively for the optimization of a directional DBS lead programming.

All participants will undergo DBS implant procedure according to standard clinical practice. After lead implant LFP will be recorded from the DBS lead for 1min in resting and hand movement states, together

with additional physiological signals. The efficacy of stimulation will be validated intraoperatively with concurrent testing of parkinsonian features and the absence of stimulation side-effects, per clinical routine.

The recorded data will be converted to Matlab (Mathworks, Natick MA) format, as described previously (Ince et al, 2010) for further analysis. The LFP data will be processed offline, using state-of-the-art signal processing and spectrum estimation techniques, to identify novel neuro-markers that will be used for the prediction of prediction of optimal stimulation contacts and correlation with the symptoms of the patient.

We will quantify the relief of symptoms through steered stimulation by contrasting the UPDRS scores before and after DBS in the outpatient clinical settings according to procedures described in the PROGRESS study for both directional and omnidirectional stimulation, and for identification of the therapeutic window.

In total, 8 patients undergoing bilateral STN DBS and part of the PROGRESS study will be enrolled for this investigation over a 1-year period. The current surgical case load at BCM supports this level of enrollment.

This study will be conducted in two centers in the U.S.A.

5.2 Objectives

5.2.1 Primary Objectives

To determine whether intraoperative LFPs recorded from the segmented DBS electrode can predict the optimal stimulation parameters.

Studies measuring and analyzing the LFPs in the STN indicate that excessive synchronization of oscillatory activity exists in the beta frequency band (8–30Hz) and can be used as a possible pathophysiological marker of the Parkinsonian state in human patients with PD (Brown et al., 2001; Williams et al., 2002; Kuhn et al., 2005). It is well recognized that PD patients in the “off” medication state demonstrate increased power in beta band oscillations at rest in both the STN and the GPi (Brown and Williams, 2005). Levodopa intake, and subsequent motor improvement, correlates with the power decrease of the beta band in both the STN (Kuhn et al, 2009) and GPi (Brown et al, 2001). However, limited research explored the functional use of LFPs for the optimization of DBS in the clinical setting. The latest research executed on a small population of human subjects indicates that the LFP activity recorded post operatively can serve as a neuro-biomarker to predict the optimal contact for stimulation (Ince et al., 2010).

With this motivation, the LFPs recorded from the contacts of the segmented DBS electrode located in the STN will be used to investigate whether the assessed activity during the surgery can be correlated with the magnitude of symptom severity and improvement following stimulation. Specifically, through a blinded study, we will investigate whether the contacts with excessive LFP activity at various bands seen intra-operatively match the contacts selected clinically for DBS programming. If they do not match, contributing factors will be explored. A sample dataset representing the predictive capability of intra-operative STN LFPs to select the clinically optimal stimulation contact is given in Fig.2.

5.2.2 Secondary Objectives

Compare the therapeutic window for stimulation delivered through directional and conventional leads and determine if the spatio-spectral LFP patterns correlate with the presence of stimulation side effects.

As one experimenter adjusts the stimulation parameters, a blinded rater will record the therapeutic window (TW) from the minimum amount of current required to provide a meaningful improvement in motor symptoms to the maximum current that could be delivered without producing adverse effects, such as dysarthria, focal muscle contractions or paraesthesias. The TW of directional stimulation will be compared to omnidirectional stimulation. Using this data (acquired through long-term directional and

omnidirectional programming as part of the PROGRESS study), as well as the 3D distribution of the LFP recordings, we will investigate the relationship between the two when an omnidirectional stimulation field is generated. For example, a side effect may be more likely to occur if the clinical stimulation field includes an area outside the spatial distribution of LFPs with select characteristics.

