5.3.1 Primary Endpoint

Concordance between LFP derived predictions and clinically optimized stimulation parameters

In this project we will establish the feasibility of recording LFP data intra-operatively from DBS electrode contacts using a multi-channel, high throughput data acquisition system and investigate if patterns in LFP can be used to select the optimal contacts for patient programming. Establishing the role of identifying and localizing LFP patterns intraoperatively can play an essential role in assisting the clinician who is programming the patient to select the optimal contact, especially when electrodes with multiple contacts (>8) are employed during DBS therapy. In this scenario, conventional techniques employing systematic contact evaluations in various combinations will be impractical due to time constraints.

The recently developed directional lead of SJM with 1-3-3-1 configuration offers the possibility of recording LFP activity from multiple directions. The primary utility of the segmented electrode is to steer the stimulation such that the side effects can be minimized. However, multiple contacts (n=8) on the electrode increase the programming complexity. In this project, we aim to determine in a blinded manner whether LFPs can guide programming. The outcomes of this pilot project will establish the scientific basis for whether LFPs recorded from a segmented electrode can be used for clinical decision making and to fine tune stimulation parameters.

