7.1.2 Secondary [Safety/Effectiveness] Endpoint Hypothesis(es)

Compare the therapeutic window for stimulation delivered through directional and conventional leads and determine if the spatospectral LFP patterns correlate with the presence of stimulation side effects.

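### Section 5.2.2 describes the LFP versus side-effect analysis only under omnidirectional stimulation, so as written it has no within-lead contrast between directions

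*Combined protocol and SAP*

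**What the plan says.** The secondary hypothesis in section 7.1.2 is to "determine if the spatospectral LFP patterns correlate with the presence of stimulation side effects". The secondary endpoint in 5.3.2 is worded just as openly. Neither names a stimulation mode, and 7.1.2 gives no method of analysis.

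The only description of the analysis is in 5.2.2. It takes as data the therapeutic-window readings from directional programming over the long term, together with "omnidirectional programming as part of the PROGRESS study), as well as the 3D distribution of the LFP recordings", and then states "we will investigate the relationship between the two when an omnidirectional stimulation field is generated". Its example is that "a side effect may be more likely to occur if the clinical stimulation field includes an area outside the spatial distribution of LFPs" with particular characteristics; there the mode of the field is not named.

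Two other places matter:

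- Section 6.3.1 records LFPs from all 8 contacts of the 1-3-3-1 lead.
- The Fig. 1 legend in section 3 says: "The therapeutic window will be studied with the implanted electrode by generation of the stimulation with 6 unidirectional and one omnidirectional pattern". The legend's next sentence, on the outcome of the unidirectional tests, breaks off in the text available for review.

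**The concern.** The objective concerns spatial LFP patterns on a lead built for steering. Section 5.3.1 says: "The primary utility of the segmented electrode is to steer the stimulation such that the side effects can be minimized". Hypothesis (a) in section 3 is that steering produces fewer side effects than omnidirectional stimulation.

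An omnidirectional field activates the segments of a level together and yields one side-effect limit for that level. LFP differences between the three segments then have no matching outcome differences on the same lead. Any correlation must come from differences between leads and between patients, where lead position and overall LFP amplitude also vary. Such a correlation would be hard to attribute to direction.

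The upper end of the therapeutic window, as 5.2.2 defines it, is the highest current free of adverse effects. Directional window data therefore contain side-effect limits for directional stimulation. The described analysis does not say that these limits will be set against the LFP of the same direction.

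**Working it through.** The plan has no power-based figure to reproduce. Section 7.1.1.2 sets the sample at 8 patients to capture heterogeneity and declines a power calculation. The check is a comparison of wording, then a count.

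**Wording**

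| Place | Limited to omnidirectional? |
|---|---|
| Aim 2 (1.1, section 2, 7.1) | No |
| Secondary endpoint (1.5.2, 5.3.2) | No |
| Secondary hypothesis (7.1.2) | No; no method given |
| Data source (5.2.2) | No; directional and omnidirectional |
| Described analysis (5.2.2) | Yes |

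**Counts**

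Inputs: 8 bilateral patients (5.1); 6 unidirectional patterns and 1 omnidirectional pattern (Fig. 1 legend); two levels of three segments (1-3-3-1 lead). Assumptions: the six patterns are one per segment, and the full set is recorded on every lead.

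- Leads: 8 × 2 = 16.
- Omnidirectional limits: 16 × 1 = 16. Within-lead degrees of freedom for direction: 16 × (1 − 1) = 0.
- Unidirectional limits: 16 × 6 = 96. Within-lead degrees of freedom: 16 × (6 − 1) = 80.
- Same-lead, same-level sets of three: 16 × 2 = 32. Degrees of freedom within lead and level: 32 × (3 − 1) = 64.
- Per patient: 96 / 8 = 12 limits in 32 / 8 = 4 sets.

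If both segmented levels were tested omnidirectionally, there would be 16 × 2 = 32 limits, still with no contrast between directions within a level.

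**Illustration of precision**

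My assumptions are a two-sided test at 0.05 and 80% power; 7.3 gives the 0.05 but not the sidedness. The smallest detectable correlation by Fisher z is tanh((1.960 + 0.842) / √(n − 3)).

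- 16 independent leads: tanh(2.802 / √13) = 0.65.
- Two leads per patient, intraclass correlation (ICC) 0.1 to 0.9 (assumed): effective n = 16 / (1 + ICC), or 14.5 to 8.4, giving 0.68 to 0.83.
- Within-lead contrast, 80 degrees of freedom: tanh(2.802 / √78) = 0.31.
- Within lead and level, 64 degrees of freedom: tanh(2.802 / √62) = 0.34.

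The last two are best cases. They assume the full test set, a common slope across patients and independent residuals. The 96 limits are not 96 independent units. For a predictor constant within a patient, effective n is 96 / (1 + 11 × ICC): 45.7 at ICC 0.1 and 8.8 at ICC 0.9. The gain is specific to contrasts between directions on the same lead.

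**The case against.** A reader might infer three stronger claims, and the documents support none of them.

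**That omnidirectional stimulation carries no directional information.** The plan compares the field with a 3D LFP distribution (5.2.2) and establishes the orientation of the segments from merged imaging (7.1.1.1). The rater looks for distinguishable effects such as dysarthria, muscle contraction and paraesthesia (5.2.2), and 6.3.1 links low-threshold effects to particular neighbouring structures. Type of effect combined with known orientation says something about direction. The 5.2.2 example, a field reaching beyond the LFP-defined area, is also a coherent question for a field that spreads all round. What is missing is the within-lead contrast between directions.

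**That the unidirectional tests are left out.** Directional programming is named as an input in the same sentence, and the endpoint and hypothesis are unrestricted. The Fig. 1 sentence on the unidirectional outcomes is cut off in the available text, which cannot count as an omission by the plan. The directional data also have a stated use in the comparison of therapeutic windows, which bears on hypothesis (a).

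**That 96 limits are certain to exist.** The six patterns appear in the Fig. 1 testing of the implanted lead, whereas 5.2.2 relies on long-term programming in the PROGRESS study, whose procedures are not in the documents. These may be different datasets, and Table 2 lists no therapeutic-window testing.

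It can also be said that guiding steering is not in the wording of the secondary objective, and that this is an exploratory pilot in eight patients. Both are fair and limit the weight of the point. They do not remove the mismatch. If directional limits are meant to enter the analysis, the sentence is too narrow; if not, a more informative comparison in data the plan already names goes unused. Pilot status does not excuse this, since 7.1.1.2 says the results should inform a later, more detailed protocol.

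**Conclusion.** The concern holds in a limited form. The LFP versus side-effect analysis described in 5.2.2 is narrower than the aim, endpoint and hypothesis it serves. Followed as written, it has no within-lead contrast between directions and depends on comparisons between leads and patients. Some directional information survives, so the analysis is weakened for a directional question rather than empty. No figure in the plan is wrong.

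The size is 0 against at most 64 degrees of freedom for direction within lead and level, or 16 omnidirectional limits against at most 96 unidirectional ones. This is conditional on the Fig. 1 set being recorded in full on all 16 leads, and everything is clustered in 8 patients. The point does not threaten the study, but it should be corrected before the LFP and side-effect data are examined together.

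**What to change.** Amend 5.2.2, and give 7.1.2 a matching method, to state that:

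1. Wherever a side-effect limit is recorded for a single segment or direction, it is paired with the LFP features of that segment.
2. The pairs are compared within lead and level, and the results are summarised per patient, so that the patient is the unit for any inference.
3. The omnidirectional analysis against the 3D LFP map is kept alongside.
4. The dataset is named: the Fig. 1 testing, the PROGRESS programming, or both with their roles distinguished.

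No testing is added. The cost is wording and some further analysis. The downsides are that clustered readings must be handled within patient, and that the comparison can use only the directional limits actually recorded. The report should therefore state how many limits and complete sets of three were available per lead.

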5.3.2 Secondary Endpoint

Characteristic of the LFP signals correlating to presence of side effects.

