7.1.1.2 Sample Size Determination

Performance of a power calculation is not relevant to the type of study proposed. Our previous studies demonstrate heterogeneity in the LFP patterns of PD subjects. The reasons for these differences are not well understood. Accordingly, we have designed this project as a pilot project to demonstrate the feasibility of the approach to analyzing spatospectral LFP patterns using a segmented electrode and exploring the relationships to clinical outcomes. A sample size of 8 was chosen to capture enough heterogeneity in order to develop a more detailed investigative protocol in the future with well-defined sample sizes based on the present observations.

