7.3 Multiplicity

All statistical tests will be conducted using a Type I error of 0.05, unless stated otherwise. Family-wise error will be adjusted accordingly.

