7.4 Overall Sample Size

A sample size of 8 was chosen to capture enough heterogeneity in order to develop a more detailed investigative protocol in the future with well-defined sample sizes based on the present observations.

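### If Aim 2 relates side effects to the stimulation field reaching outside the LFP region, current drives both, so an association tends to appear even when the LFP map is uninformative

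*Combined protocol and SAP*

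**What the plan says.** The secondary endpoint (5.3.2) is "Characteristic of the LFP signals correlating to presence of side effects", and 7.1.2 sets the task as to "determine if the spatospectral LFP patterns correlate with the presence of stimulation side effects". Neither names a statistic, a unit of analysis or any handling of current.

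Section 5.2.2 has a blinded rater record the therapeutic window in units of current. Its upper limit is "the maximum current that could be delivered without producing adverse effects". These data, together with the 3D LFP distribution, are to be related under omnidirectional stimulation. The one concrete illustration, introduced as an example, is that side effects may be likelier "if the clinical stimulation field includes an area outside the spatial distribution of LFPs with select characteristics". The LFP characteristics that define that region are not specified.

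On size and error control, 5.1 says "In total, 8 patients undergoing bilateral STN DBS and part of the PROGRESS study will be enrolled". Section 7.1.1.2 says "Performance of a power calculation is not relevant to the type of study proposed", and 7.3 says "All statistical tests will be conducted using a Type I error of 0.05, unless stated otherwise".

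**The concern.** Spill-out is built from two ingredients: the LFP map, and the size of the stimulation field. Aim 2 concerns the first. For a given contact the second grows with current, and section 3 attributes side effects to stimulation spreading into neighbouring structures. Raising the current therefore makes both spill-out and side effects more likely.

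A plain test of spill-out against side effects, run over observations with different currents, mainly asks whether current matters. The question Aim 2 needs answered is whether the LFP map adds anything at a given current. No section holds current fixed, adjusts for it, or uses a comparison map.

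Sections 7.1.1.2 and 7.4 say this pilot will shape a later protocol, and 7.2 says its outcomes will support a judgement on using LFPs in clinical decisions. An effect of stimulation strength reported as LFP information would carry into both.

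**Working it through.** The plan gives no figure to reproduce: the sample size has no effect size, power or formula behind it.

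**Inputs from the documents.** 8 patients with bilateral leads, so up to 8 × 2 = 16 leads with the patient as the independent unit (5.1); test level 0.05, sidedness not stated, two-sided assumed (7.3); window limits recorded as currents (5.2.2).

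**Step 1: direction, from the definitions.** Take one lead and one omnidirectional contact configuration. The lower window limit is below the side-effect current; the side effect appears just above the upper limit. Because the field is larger at the upper limit, a lead can go from no spill-out to spill-out between the limits, but never the reverse. Every lead whose spill-out status changes points the same way, whatever its LFP map. In a sign test over patients:
- 6 patients changing: two-sided p = 2 × (1/2)^6 = 0.031.
- 5 patients changing: two-sided p = 2 × (1/2)^5 = 0.0625.

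Six of the 8 patients changing status is thus enough for nominal significance with an uninformative map.

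**Step 2: why the size depends on geometry.** Assumptions, none from the documents: field radius = k × √(current in mA) mm; LFP extent mean 2.5 mm (SD 0.5); side-effect threshold mean 3.5 mA (SD 0.8). The field passes the mean extent at (2.5/k)² mA:
- k = 1.0: 6.25 mA, which is (6.25 − 3.5)/0.8 = 3.4 SD above the mean threshold, so almost no field spills.
- k = 1.5: 2.78 mA, a little below the mean threshold, so many leads change status.
- k = 2.0: 1.56 mA, so fields spill early, and a change depends on where the lower limit lies.

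**Step 3: rejection rate with extent drawn independently of threshold (nominal 5%).**

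| Comparison | Rejection |
|---|---|
| Two window limits per lead, nine k/extent settings | 71-100% in six; 0-17% in three where nearly all or almost no fields spill |
| All titration steps (0.5-5 mA), patient-level test, same nine settings | 94-100% in seven; 45% and 0.3% where almost no field spills |
| One setting per lead, amount of spill-out, current independent of threshold (SD 0.8 mA) | 12-28% |
| The same, current SD 0.5 / 1.1 mA | 5-11% / 20-47% |
| One setting per lead, yes/no spill-out (Fisher) | 0-11% |
| One common current | 0.7-3.1% |

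A second set of six scenarios (k = 1.6; threshold mean 3-4 mA, SD 0.5-1.5; extent mean 2.5-3.2 mm, SD 0.4-1.0) agreed in direction. Pooling all steps, side-effect risk in its base case was 67% with spill-out and 20% without (odds ratio 7.8; range over scenarios 3.7-34.6). A patient-level test rejected 90-100%, so clustering alone is not the explanation. Yes/no spill-out at one setting per lead rejected 3-11% in five scenarios and 32% in the one where threshold and extent varied little.

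**Step 4: current-free alternatives under the same null.** Patient-level correlation of LFP extent with threshold current rejected 3-7%. Reassigning LFP maps between patients, both leads together, rejected 0-7%. Stratifying by current while treating repeated settings as independent still rejected 13-30%, so the patient must be the unit as well.

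**Step 5: what 8 patients can detect.** At a true correlation of 0.8 between extent and threshold, power was 0.75 for the correlation and 0.81-0.92 for map reassignment; at 0.9, 0.94 and 0.93. For the correlation test, power is about a quarter at 0.5 and under 40% at 0.6.

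**The case against.** The spill-out sentence is an example of a hypothesis, not a specified predictor or test. The endpoint in 5.3.2 contains no field size. The sentence before the example can be read as relating the window currents directly to the LFP distribution, which is close to the current-free analysis recommended here. All of this stands, so a reader who inferred that the plan commits to a spill-out test would be going beyond the text.

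A reader might also infer that Aim 2 is almost certain to give a false positive. The documents do not support that either. They have the rater record a window, and do not describe pooling every titration step. The example speaks of the clinical field, which may mean one setting per lead. At one setting with yes/no spill-out the inflation is mostly small. If clinical current is set relative to the patient's own threshold (assumed mean 85% of it, 15% scatter), amount of spill-out rejects only 4-8%, though 25% scatter brings back 12-27%. If settings stay safely below threshold, side effects hardly occur and the question cannot be answered.

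Window procedures follow the PROGRESS study (6.3.2), and section 7 allows a separate SAP. Neither is available, so step structure and any matching on current cannot be judged.

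These points limit the size of the concern but do not remove it. Section 5.2.2 says the data for this analysis are the window data, in which current varies by design. Comparing only the two recorded limits is enough to produce the artefact, and no other method is given.

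**Conclusion.** The concern holds conditionally. If spill-out is compared across settings that differ in current, an association with side effects is to be expected even with an uninformative LFP map. The direction follows from 5.2.2's own definitions plus one physical premise, that the field grows with current at a given contact.

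The size rests on assumed geometry, thresholds and choice of settings: about 70-100% false positives in most assumed geometries for the two window limits or all titration steps; 12-28% for amount of spill-out at one setting per lead with current independent of threshold; 0-11% for yes/no spill-out at one setting in most scenarios; none at a common current.

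It would be wrong to infer that the trial's conclusions are invalid. This is an unpowered pilot, and no decision rule in the plan uses this association. The consequence is a misleading exploratory signal for the next protocol, not a wrong confirmatory result. The change is still worth making, because the only comparison the plan illustrates is the biased one and the data for a better one are already planned.

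**What to change.** In 5.2.2 and 7.1.2, make the LFP comparison free of current, with the patient as the unit, by one of two routes:

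- Relate LFP extent around the lead, with no field size in it, to the side-effect threshold current, averaging the two leads of each patient.
- If spill-out is used, keep each patient's currents and side effects as observed, and test against a reference distribution from reassigning LFP maps between patients, moving both leads together. The LFP map is supported only if a patient's own map explains side effects better than other patients' maps at the same currents.

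These are alternatives, not equivalents: the first reduces a 3D map to a single extent. Either needs the LFP characteristics that define the region to be stated. Report the raw spill-out association as descriptive only.

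The cost is a paragraph of analysis text and, for the second route, a short permutation program. The window currents, side effects and LFP recordings are already planned, so no extra patients or visits are needed. The downside should be stated in the plan: the reported association will be less striking, and with 8 patients only strong relations (correlation about 0.8 or more) are likely to be detected.
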